**IRB#: 09-060 A(4)**

number of samples from each tumor that represent differential features. For larger sample sets, simple Venn intersection may reveal core signature genes. Sparser samplings of feature contrasts will be analyzed by pairwise Gene Set Enrichment to identify a subset of mutually expressed signature genes.

Analysis of gene signatures: Gene signatures representing contrasting imaging features will be compared with known signatures representing previously described molecular subclasses of GBM, including the "Proneural", "Proliferative" and "Mesenchymal" classes, as well as molecular subclasses already emergent in the analysis of 206 GBM samples in The Cancer Genome Atlas pilot project to date. Signatures will be compared by GSEA and gene ontology. GSEA will also be used to analyze feature-derived signatures in an exploratory process to characterize possible enrichment for altered expression within canonical pathways. The Connectivity Map offers another potentially valuable resource for mining feature-derived signatures, and can be approached with specific hypothesis: that differential proliferation and permeability, as image-derived features, may be associated with transcriptome evidence of PI3 kinase signaling or VEGF signaling, both of which are well represented in the database. Analysis will include exclusion of gene subsets such as cell cycle members whose differential regulation is likely to correlate with simple histologic measures of proliferation.

For the exploratory aim, we can evaluate the power we will have to detect a difference in gene expression levels between areas of high and low tracer uptake (or signal intensity) within an individual. With 15 subjects contributing a sample from both a high and low uptake area, we expect to be able to detect a twofold difference in base 2 log intensity levels with a Type I error of 0.001 and a Type II error of 0.05 if the standard deviation for the expression levels is 0.75 (using base 2 logarithms) or less. A standard deviation of 0.75 is within the range of what we expect to see.

Sample size justification:

For this pilot study, we expect there to be 15 eligible patients per year, and we will aim to reasonably accrue 8 of these patients per year for two years.

All analyses are purely exploratory and intended to generate data for future studies. We do not plan to conduct any rigorous hypothesis testing. To explore what we might be able to say using this limited sample size, we find that with data on 15 patients we expect to be able to detect a moderately high correlation coefficient of 0.60 with 80% power using a two-sided 0.05 level test. This calculation assumes that each patient contributes only one observation, but in our case, we expect an average of two observations for each patient (up to four samples per patient) which may increase our power to draw any conclusions. Simulation studies assuming an average of two observations per patient indicate that we can estimate the concordance correlation coefficient to within (half-width of 95% confidence interval)  $\pm 0.27$  for a CCC equal to 0.8,  $\pm 0.20$  for a CCC equal to 0.9, and  $\pm 0.05$  for a CCC equal to 0.99.

**Memorial Sloan-Kettering Cancer Center  
IRB Protocol**

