Exploratory Aim Study Design: Biopsy samples will be acquired from regions of increased/decreased proliferative activity (FLT uptake). Gene expression from microdissected portions will be assayed by Affymetrix U133Plus2 arrays. Differential gene expression signatures will be derived for each pair of samples in a resection, representing differences between FLT uptake values. Signatures will be compared across samples to attempt to characterize a core signature. Core signatures will be investigated by comparison to known transcriptome signatures of molecular subclasses of GBM as well as compared with other pathways and signatures.

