Statistical Methodology for Exploratory Aim:

ACGH: Array CGH data will be analyzed through the software pipeline developed within MSKCC's Cancer Genome Characterization Center within The Cancer Genome Atlas Project. This includes extensive QC annotation, normalization and artifact reduction, and segmentation analysis.

Expression analysis for gene signatures: Expression array data will be normalized by RMA and differential expression of paired samples determined by Significance Analysis of Microarrays (SAM). Methods of analysis cross-sample will aim at determining core signature genes which are commonly differentially expressed in relation to imaging features. These methods will depend on the

**Memorial Sloan-Kettering Cancer Center  
IRB Protocol**

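### The exploratory gene-expression analysis builds lists from single pairs, where SAM has no variance to work with, and never specifies the pooled 15-pair comparison that its power statement assumes

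*Combined protocol and SAP*

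**What the plan says.** Section 4.2 (Exploratory Aim Study Design) sets the unit of analysis: "Differential gene expression signatures will be derived for each pair of samples in a resection". The next step is a comparison of those signatures: "Signatures will be compared across samples to attempt to characterize a core signature".

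Section 11.0 (Statistical Methodology for Exploratory Aim) names the test: "differential expression of paired samples determined by Significance Analysis of Microarrays (SAM". It treats the search for core genes as a separate step, and makes the choice of method depend on how many contrasting samples each tumor yields. For the richer case, which it calls the larger sets, "simple Venn intersection may reveal core signature genes". For the other: "Sparser samplings of feature contrasts will be analyzed by pairwise Gene Set Enrichment". No fold-change cut-off, SAM delta, false discovery rate or required number of overlapping lists is given.

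The power statement in the same section describes something else, one within-patient comparison over the whole cohort: "With 15 subjects contributing a sample from both a high and low uptake area", able to "detect a twofold difference in base 2 log intensity levels" with type I error 0.001, type II error 0.05 and a standard deviation of at most 0.75 in log2 units. The sample size paragraph expects about two samples per patient and at most four.

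**The concern.** SAM divides a gene's mean difference by an estimate of that gene's variability and judges the result by permutation. A patient with one high-uptake and one low-uptake sample supplies one difference per gene, hence no variability estimate and almost nothing to permute. A list from such a pair can only be a ranking or cut on raw fold change.

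Combining the lists by intersection then turns the number of lists into a handicap: each further list is another chance for a truly changed gene to miss the cut. A pooled analysis works the other way and gains precision with each pair.

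The aim asks whether high and low proliferative areas differ consistently. A rule that can drop consistently changed genes bears on exactly that question, and the results are meant to inform later studies. The power statement offers no reassurance, because it applies to an analysis that the methods text does not set out.

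**Working it through.** **Inputs from the plan.** 15 pairs; twofold difference, read as 1.0 on the log2 scale; SD 0.75; type I error 0.001 (sidedness not stated); power 0.95. The plan does not say whether 0.75 is the SD of a single sample or of the within-pair difference.

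**1. The plan's own figure.** Take 0.75 as the SD of the difference and use the paired normal formula, two-sided:

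- n = ((3.29 + 1.645) × 0.75 / 1)² = 13.7, so 14 pairs (plan: 15).
- Power at 15 = Φ(√15 / 0.75 − 3.29) = Φ(5.16 − 3.29) = 96.9% (plan: 95%).

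The statement reproduces as one paired test over all 15 patients. With the exact noncentral t (14 df, noncentrality 5.16), power is 80.7%. If 0.75 is a per-sample SD and the two samples are uncorrelated, the difference SD is 0.75 × √2 = 1.06, the noncentrality is √15 / 1.06 = 3.65, and exact power is 37.4%.

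**2. What one pair gives SAM.** One difference has 1 − 1 = 0 degrees of freedom, and there are 2 label arrangements. Fifteen pooled pairs have 14 df and 2¹⁵ = 32,768 sign arrangements. At the maximum of four samples split 2 v 2 in one tumor, there are 2 df and 6 arrangements. With a per-sample SD of 0.75 / √2 = 0.53, a t-test there has 20% power at 0.05 and 0.5% at 0.001.

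**3. Intersection of single-pair lists.** The cut-offs here are assumptions, as is independence between patients. The chance that one list contains a gene with true log2 difference 1 and difference SD 0.75 is:

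- twofold cut-off (log2 = 1): Φ(0) = 0.50;
- 1.5-fold cut-off (log2 = 0.585): Φ(0.415 / 0.75) = 0.71.

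The chance of being in all k lists is that value to the power k:

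| Lists | Twofold cut-off | 1.5-fold cut-off |
|---|---|---|
| 3 | 12.5% | 36% |
| 5 | 3.1% | 18% |
| 8 | 0.4% | 6.5% |
| 15 | 0.003% | 0.59% |

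**4. Sensitivity of these results.**

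- *Larger effect.* A fourfold gene (log2 = 2) survives 15 lists with probability 24% (twofold cut-off) to 64% (1.5-fold cut-off).
- *Two sites averaged per class, independent errors.* The difference SD falls to 0.53. The twofold cut-off still gives 0.50 per list, because the cut equals the true mean. The 1.5-fold cut-off gives Φ(0.415 / 0.53) = 0.78, hence 48% over 3 lists, 29% over 5 and 2.6% over 15.
- *Looser overlap rule.* At least 8 of 15 lists keeps the twofold gene with probability 50% (twofold cut-off) to 96% (1.5-fold cut-off), by the binomial tail.

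**The case against.** The best reply is that the plan already intends the pooled analysis. The SAM sentence speaks of paired samples without saying that each pair is tested alone, and the power statement describes 15 patients together. That is a fair reading of intent. However, Section 4.2 derives signatures pair by pair, and Section 11.0 follows SAM with a list-combining step, which presupposes several lists. The pooled test is implied only by a power calculation, so the sections need reconciling.

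Three stronger conclusions are tempting, and the documents do not support them:

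- *That a gene must pass in every patient.* No overlap rule is stated, and the intersection is worded as something that may help. The 15-list row is an extreme case.
- *That the plan sends intersection to the setting where it does worst.* The larger sets in that sentence are sets with more samples per tumor, not more patients. A patient with a single pair is the sparse case and goes to gene set enrichment. If only a few richly sampled tumors were intersected, the rows for 3 and 5 lists are nearer the mark.
- *That a true signature would almost always be missed and reported as absent.* Enrichment, gene ontology and Connectivity Map analyses stand beside the intersection, and nothing says that an empty overlap would be reported as a negative finding.

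The comparison is also not like for like. Strict 15-list intersection has a far smaller false-positive rate than a test at 0.001, so part of the gap is stringency. At the 1.5-fold cut-off, a 10-of-15 rule keeps the twofold gene with probability 75%, and keeps an unchanged gene in that direction with probability 0.00024. That is close to the pooled test (81%, with 0.0005 per direction). A well-chosen rule could therefore do nearly as well, but the plan chooses none.

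**Conclusion.** The point holds as one of specification and choice of method. As written, per-pair SAM has no valid statistic in a patient with the expected two samples, and the comparison that the plan powers is never named as the analysis. Strict intersection loses sensitivity with each added list. How much depends on cut-offs that the plan does not give, on the overlap rule, and on the reading of 0.75. At the planned effect the loss is already marked at 3 to 5 single-pair lists, while the pooled test retains between 37% and 81% power on the two readings of the SD. Section 11.0 describes all analyses as exploratory and disclaims rigorous hypothesis testing. The consequence therefore stays within the exploratory aim and does not touch the primary or secondary aims.

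**What to change.** In Sections 4.2 and 11.0, make one paired (one-class) SAM across patients the main core-signature analysis. The input is each patient's high-minus-low log2 difference, with the patient as the unit. Average sites within class when a patient has more than one, and state the false discovery rate. Keep per-patient lists, Venn overlap and pairwise gene set enrichment as descriptive checks of consistency. If overlap is reported, give the cut-off and the number of lists required in advance. State also whether the 0.75 in the power statement refers to a single sample or to the within-pair difference.

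The cost is wording only. The arrays, the number of patients and the software stay the same, and the analysis then matches the comparison that the plan powers.

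### In the exploratory gene-expression power statement, an SD of 0.75 or less is not a sufficient condition for a Type II error of 0.05: neither the SD nor the test is defined

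*Combined protocol and SAP*

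**What the plan says.** The statement is in Section 11.0 Biostatistics, at the end of the methodology for the exploratory aim. It concerns a "difference in gene expression levels between areas of high and low tracer uptake (or signal intensity) within an individual". The design input is "With 15 subjects contributing a sample from both a high and low uptake area". The claim is that the study can "detect a twofold difference in base 2 log intensity levels with a Type I error of 0.001 and a Type II error of 0.05", and the condition attached is "if the standard deviation for the expression levels is 0.75 (using base 2 logarithms) or less". In support the plan adds "A standard deviation of 0.75 is within the range of what we expect to see", citing a paper on microarray study design.

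The plan does not say:
- which test or formula gave the figure, or whether it is one- or two-sided;
- whether 0.75 is the SD of one sample or of the high-minus-low difference within a patient;
- what within-patient correlation is assumed.

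Earlier in the same methodology, the analysis planned for the paired samples is Significance Analysis of Microarrays (SAM). The sample size justification that follows says "All analyses are purely exploratory and intended to generate data for future studies".

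**The concern.** The comparison is made within patients, so power is governed by the SD of the within-patient difference. The plan's wording points instead to the SD of the expression levels. For two samples with equal SDs, the two quantities coincide only when the within-patient correlation is 0.5. A reader cannot tell which was used, and power differs greatly between the possibilities.

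Even on the simpler reading, a Type I error of 0.001 with only 14 degrees of freedom is far into the tail, where normal and t critical values differ widely. A figure from a normal formula can therefore be well above what a t-test delivers.

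A Type II error of 0.05 says that about 5 in 100 genes with a true twofold change would be missed. If the real figure were several times higher, anyone using these pilot data to plan a later study would place too much trust in 15 pairs.

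**Working it through.** **Inputs** (all from the power statement in Section 11.0): n = 15 pairs; alpha = 0.001; stated power 1 − 0.05 = 0.95; SD 0.75 on the log2 scale. Twofold is taken as delta = 1 log2 unit. Sidedness and correlation are not given, so both sides and a range of correlations are shown.

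**Step 1. Reproduce the plan's figure.** Take 0.75 as the SD of the within-patient difference and use the two-sided normal approximation.
- Standardised effect: delta × √n / SD = √15 / 0.75 = 5.164.
- Power = Φ(5.164 − 3.291) = Φ(1.873) = 0.969.
- Pairs needed for 95%: [0.75 × (3.291 + 1.645)]² = 13.7, so 14.
- Largest SD giving 95% with 15 pairs: √15 / (3.291 + 1.645) = 0.785.

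This is consistent with the statement, so there is no slip of arithmetic on this route.

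**Step 2. Same SD, ordinary paired t-test.** Power comes from the noncentral t distribution with 14 df and noncentrality 5.164.
- Two-sided: critical t 4.140 (against z 3.291), power 0.807, Type II error 0.193. A simulation of 400,000 runs gave power 0.808.
- One-sided: critical t 3.787, power 0.880, Type II error 0.120.
- Largest SD of the difference giving 95% power: 0.628 two-sided, 0.674 one-sided.
- Referring the t statistic to the z cut-off does not help: the two-sided Type I error would be about 0.0054, more than five times the stated 0.001.

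**Step 3. 0.75 as the SD of a single sample.** SD of the difference = 0.75 × √[2(1 − ρ)], with ρ the within-patient correlation. The values of ρ are assumed.

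| ρ | SD of difference | Power, two-sided t | Power, one-sided t |
|---|---|---|---|
| 0 | 1.061 | 0.37 | 0.48 |
| 0.3 | 0.887 | 0.60 | 0.70 |
| 0.5 | 0.750 | 0.81 | 0.88 |
| 0.6 | 0.671 | 0.91 | 0.95 |
| 0.65 | 0.627 | 0.95 | above 0.95 |

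Power of 95% needs ρ of about 0.65 or more two-sided, or about 0.60 one-sided.

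**Step 4. The planned method.** SAM adds a constant to the denominator of the t-type statistic. A SAM-type statistic was simulated with its cut-off calibrated to a two-sided 0.001, for a gene whose difference has SD 0.75. Power was about 0.94 to 0.95 when all genes were given the same SD, and about 0.89 to 0.96 under assumed unequal gene SDs. These values are not bounds. They depend on the constant and on the assumed spread of gene SDs, neither of which the plan gives, and a wide enough spread would lower them.

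**The case against.** The strongest reply is that no t-test is planned. SAM is, and with equal gene SDs its power comes close to the stated 0.95. This stands, and it limits the point. A reader might infer from Step 2 that the true Type II error of the planned analysis is 0.19. The documents do not support that: 0.19 belongs to an ordinary two-sided paired t-test, which would be a poor stand-in for SAM here. Equally, the plan gives no SAM settings or simulation for this figure, whereas its sample size justification does cite simulations for the concordance correlation.

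A reader might also infer an arithmetic error. Step 1 shows that a standard large-sample formula is consistent with the statement, so what is lacking is a stated basis. Under the single-sample reading, two samples from one tumour may be correlated strongly enough to give 95%: at a correlation of 0.7, two-sided t power is 0.98. The plan gives no value in either direction. The cited design paper may define the SD, but it is not part of the documents.

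"detect a twofold difference in base 2 log intensity levels" could be taken literally as 2 log2 units. Power would then exceed 0.99 even at zero correlation, far from the stated 0.95. Only the 1-unit reading comes near the plan's figure.

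Finally, the aim is exploratory, and the gene-level results feed signature and enrichment analyses, not claims that single genes are unchanged. That keeps the stakes low. It does not justify stating an error rate without the assumptions behind it.

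**Conclusion.** The concern holds in a limited form. An SD for the expression levels of 0.75 or less does not by itself give a Type II error of 0.05 with 15 pairs at 0.001.
- If it is a single-sample SD, two-sided paired t power runs from 0.37 to 0.95 over assumed correlations of 0 to about 0.65.
- If it is the SD of the difference, a normal approximation gives 0.97, but a paired t-test gives 0.81 two-sided or 0.88 one-sided. The statement then fails under a two-sided t-test for SDs from about 0.63 up to the plan's own limit of 0.75.
- For SAM the figure is neither established nor refuted.

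These results assume 15 complete pairs, normally distributed differences and a 1 log2 unit effect. A reader might go further and conclude that the study needs more patients. That does not follow: the sample size justification does not use this calculation, and no primary or secondary analysis depends on it.

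**What to change.** Rewrite the power sentence in Section 11.0 so that the SD and the test are defined. For example: With 15 complete high/low pairs, an ordinary two-sided paired t-test at alpha 0.001 has about 81% power to detect a 1 log2 unit difference if the SD of the within-patient difference is 0.75, and 95% power if that SD is about 0.63 or less; the planned SAM analysis may have higher power.

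The t-test should not be described as an approximation to SAM. If the sponsor prefers to keep 95%, the plan should support it with a SAM simulation that states the added constant, the assumed gene SDs, the sidedness and the meaning of 0.75, together with the within-patient correlation if 0.75 is a single-sample SD.

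The first option costs one or two sentences; the second adds a short simulation. Neither changes the number of patients, the assays or any planned analysis. Low priority.

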## 11.0 BIOSTATISTICS

This is a pilot study intended to collect preliminary data on 15 patients diagnosed with untreated high-grade glioma who are scheduled to undergo surgical resection.

Primary Aim: To investigate relationships between voxel-based determinations of proliferation rate and observed MR imaging features, as well as with spatially registered histologic measures of tumor cell proliferation (Ki67) and microvascular density (CD31) at corresponding locations.

Statistical Methodology for Primary Aim: In this aim, we will first explore the relationships between  $^{18}\text{F}$ -FLT PET parameters and MR imaging features ( $K_{\text{trans}}$  or microvascular permeability). The  $^{18}\text{F}$ -FLT PET parameters:  $K_1$  (tracer delivery rate constant),  $k_2$  (rate constant reflecting flow from the tumor interstitial compartment back to blood),  $k_3$  (rate constant reflecting proliferation), and  $k_4$  (rate constant reflecting flow from tumor cells back into the tumor interstitial space) will be compared to  $K_{\text{trans}}$  on MR imaging. We will also explore relationships between  $K_{\text{trans}}$ , each of the  $^{18}\text{F}$ -FLT PET parameters, and the histological markers Ki67 and CD31. All of the parameters and markers are measured on a continuous scale. Initially graphical methods such as pair-wise scatter plots will be used to assess the relationships. The relationships between each pair of variables will be more formally evaluated using methods that account for correlated data (there may be up to four observations per patient) such as random effects regression models or generalized estimating equations.

It is unlikely but possible that it may be determined at surgery that a patient does not have a high-grade glioma but instead has a metastasis or PCNSL. The likelihood that this will occur will be infrequent, if at all, given the constellation of distinctive imaging features that generally serve to differentiate these tumor types. If it does occur, however, we will continue accrual until 15 high grade glioma patients have been enrolled. In this case, two sets of analysis for the primary aim and all other aims will occur, one including all enrolled patients and one including only patients with high-grade gliomas. Patients found to have a metastasis or PCNSL may not yield different values than patients with glioma so the decision to include them in the analysis may not be unreasonable.

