**IRB#: 09-060 A(4)**

However, we will descriptively assess any differences in results between the two sets of analysis as much as the data permits if this situation arises.

Secondary Aim #1: To attempt to corroborate voxel-based parameter estimates reflecting tumor cell proliferation with estimates derived using standard ROI-based pharmacokinetic modeling methods, for improving the characterization of high-grade gliomas using dynamic  $^{18}\text{F}$ -FLT PET-CT.

Statistical Methodology for Secondary Aim #1: To corroborate the voxel-based method with the ROI-based approach, pharmacokinetic modeling will be assessed by comparing the estimated parameter values for the entire intra-tumor ROIs to the average of the voxel-by-voxel parameter values among the voxels comprising the same ROIs. This analysis will focus on the  $k_3$  value. For each ROI, we would like to see the estimated  $k_3$  value derived from the entire ROI to be within 25% of the average  $k_3$  value determined for the multiple voxels. The ratio of two  $k_3$  values will be computed for this purpose. As an additional analysis, we will calculate the concordance correlation coefficient (CCC) to evaluate the agreement between the ROI-based and the average voxel-based parameter values. A modified version of the CCC that allows for clustered data will adjust for the fact that there may be multiple observations per patient contributing to the estimates.

Secondary Aim #2: To assess whether static measures of  $^{18}\text{F}$ -FLT uptake can adequately serve as non-invasive biomarkers of proliferative activity or whether parametric images, based on compartmental analyses of the FLT pharmacokinetics, are required by correlating findings of both approaches with regional histologic assays of tumor cell proliferation.

Statistical Methodology for Secondary Aim #2: Using the same methods described for the primary arm, the relationship between Ki67 and the static measure of  $^{18}\text{F}$ -FLT (the SUV), and the parametric measure ( $k_3$ ) will be explored. The strength of the relationship between these two parameters and Ki67 will be compared descriptively.

Exploratory Aim: To evaluate whether differences in gene expression seen between areas of increased and decreased proliferative activity on parametric maps define consistent differential transcriptome signatures for comparison with known molecular subclasses of GBM and known pathways.

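### The stated 80% power to detect a correlation of 0.60 with 15 patients does not follow from its own inputs, which give about 67–70%

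*Combined protocol and SAP*

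**What the plan says.** The Sample size justification in Section 11.0 gives one power statement for correlations. For 15 patients, the authors write, "we expect to be able to detect a moderately high correlation coefficient of 0.60 with 80% power using a two-sided 0.05 level test". The next sentence fixes the unit of analysis: "This calculation assumes that each patient contributes only one observation". The authors then expect about two samples per patient, with a maximum of four, "which may increase our power to draw any conclusions".

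Three other statements set the context:

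- The same section says "All analyses are purely exploratory and intended to generate data for future studies" and disclaims rigorous hypothesis testing.
- It opens with feasibility: "we expect there to be 15 eligible patients per year, and we will aim to reasonably accrue 8 of these patients per year". Over the two-year accrual period, that comes to 8 × 2 = 16 patients.
- The methods for the primary aim say "All of the parameters and markers are measured on a continuous scale". For Secondary Aim #2 they say "The strength of the relationship between these two parameters and Ki67 will be compared descriptively".

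**The concern.** Sample size, effect size, test level, sidedness and number of observations per patient are all stated, so the power can be recomputed with no further design assumption. A correlation of 0.60 is large, but 15 pairs is few, and 80% looked too high for a two-sided test.

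The other quantitative statements in Section 11.0 concern gene expression differences and the precision of the concordance coefficient. This sentence is therefore the only guide to what the study can show about k3, SUV, K_trans, Ki67 and CD31. The text offers 80% as the one-observation figure and repeat samples as a possible gain on top. If that starting point is too high, a correlation that fails to reach significance would be taken as stronger evidence of no relationship than it is. The pilot is also meant to inform larger studies, so the figure could be carried forward.

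**Working it through.** **Inputs, all from the Sample size justification in Section 11.0:** n = 15 patients, one observation each; correlation 0.60 under the alternative (0 under the null, implied); two-sided level 0.05; stated power 80%. The document does not show its formula, so several standard ones were tried.

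**1. Fisher z approximation.** Power = Φ(atanh(r)·√(n − 3) − 1.960).
- atanh(0.60) = 0.6931 and √12 = 3.464, with product 2.401.
- Φ(2.401 − 1.960) = Φ(0.441) = **0.670**.
- Adding the usual small-sample bias term r/(2(n − 1)) to the mean gives 0.697.

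**2. t-test of r under bivariate normality (exact).** The test rejects when |r| exceeds 0.514, from the t critical value 2.160 on 13 degrees of freedom. Integrating the noncentral t over a chi-square with n − 1 = 14 degrees of freedom gives **0.701**. A simulation of 400,000 samples gives 0.702.

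**3. One variable treated as fixed by design.** This is the most favourable of the models. The noncentrality is (0.60/0.80)·√15 = 2.905 on 13 degrees of freedom, and power is **0.766**.

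None of these reproduces 0.80.

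**What would give 80%?**

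| Change | Fisher z | Exact bivariate normal | One variable fixed |
|---|---|---|---|
| None (n = 15, r = 0.60, two-sided) | 0.670 | 0.701 | 0.766 |
| n = 16 | 0.705 | 0.734 | 0.797 |
| One-sided 0.05, n = 15 | 0.775 | 0.806 | 0.865 |
| r needed for 80% at n = 15, two-sided | 0.669 | 0.653 | 0.616 |

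The number of independent observations needed at r = 0.60 is:
- Fisher z: ((1.960 + 0.842)/0.6931)² + 3 = 19.3, so 20.
- Exact: power is 0.790 at n = 18 and 0.814 at n = 19, so 19.

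Two routes come close to the stated figure. One is a one-sided test at n = 15 (80.6% exact), which contradicts the stated sidedness. The other is 16 patients with one variable treated as fixed (79.7%), which contradicts the stated n and suits two measured quantities less well.

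**The case against.** The strongest reply is that the figure does little work and that actual power may be adequate. Fifteen patients is a feasibility number, the analyses are declared exploratory, Secondary Aim #2 is compared descriptively, and no threshold or decision depends on the 80%.

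The one-observation case is also a simplification. Take 15 patients with two observations each, a correlation of 0.60 both between and within patients, equal intraclass correlation in both variables, and a critical value calibrated under the null. Simulated power is then about 0.91 at an intraclass correlation of 0.5, 0.85 at 0.7, 0.81 at 0.8, 0.76 at 0.9 and 0.70 at 1. Biopsy sites are chosen for heterogeneity, which argues against extreme similarity within a patient. This stands as a limit on the practical weight: the planned analysis may well exceed 80%. It does not rescue the sentence, which leaves repeat samples out of its calculation and mentions them only as a possible gain. The plan gives no within-patient correlations from which that gain could be worked out.

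A second reply concerns method. The planned formal analyses are regression models, which ordinarily condition on a covariate, and the fact that all variables are continuous does not rule out the fixed-variable calculation. That is fair, and it widens the range to 67–77%. The top of that range still falls short of 80% at the stated n, and for a correlation between two measured quantities the bivariate-normal result is the more natural planning figure.

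A third is that the slip may lie in the word two-sided and not in the 80%. The one-sided result makes this plausible, but the documents cannot confirm it, and the sentence would be wrong as written either way. The power-analysis text cited for the figure was not available; the check does not need it.

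**Conclusion.** The concern holds. With 15 independent pairs, a true correlation of 0.60 and a two-sided 0.05 test, power is 67% (Fisher z) to 70% (exact bivariate normal), and 77% at most if one variable is taken as fixed. The stated 80% is too high by 10 to 13 percentage points on the standard correlation methods and by about 3 on the most favourable model. The type II error in the stated scenario is about 30–33%, not the implied 20%.

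The conclusion rests only on the plan's own inputs and, for the exact figure, on bivariate normality. It does not show that the planned clustered analysis is underpowered, because that depends on within-patient correlations the plan does not give. The error should be corrected, but its consequences are modest.

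**What to change.** Keep 15 patients and the two-sided test, and replace the power sentence with wording such as:

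> With a single observation from each of 15 patients, a two-sided test at the 0.05 level has about 70% power if the true correlation is 0.60; 80% power requires a true correlation of about 0.65 to 0.67.

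Name the method used (exact bivariate normal or Fisher z). If the 80% came from a one-sided calculation, the authors should say so and still report the two-sided value, since that is the test the plan names.

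Keep the remark that repeat samples may add power, and add that the gain depends on the within-patient correlation of both variables, which is not known in advance.

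The cost is one sentence and one clause in Section 11.0, and a slightly less favourable figure. Design, sample size and analysis do not change.
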